Our long-term goal is to develop a clinically useful, exercise intervention that can serve as an alternative to facility-based programs, with the objectives of alleviating fatigue, forestalling disability and improving prognosis. Our objective in this application is to determine whether exercise training via neuromuscular electrical stimulation (NMES) has beneficial effects on skeletal muscle size and function in cancer patients. We hypothesize that NMES will improve skeletal muscle size, contractile function and oxidative capacity, based on our seminal observations in cancer patients that functional disability derives, in part, from deficits in skeletal muscle contractile protein and mitochondrial content and function, as well as our data showing that NMES counters such deficits. Our rationale underlying this proposal is that establishing proof-of-principle, mechanistic evidence for the utility of NMES to remediate these skeletal muscle deficits in cancer patients receiving treatment will provide a solid foundation upon which to support more definitive trials of the utility of NMES in the cancer survivor population.

We will use data from cancer patients studied prior to and 8 weeks following completion of NMES or control intervention on lower extremity musculature, with muscle structure and function being measured across a range of anatomic levels. We focus on testing our hypotheses with cellular and organellar level measurements because they permit a more rigorous evaluation of the effects of NMES on muscle biology by circumventing limitations in the detection of exercise effects at the whole body or whole muscle level due to methodological shortcomings, subjective motivation and, specific to NMES, effects on neural activation. Determination of the utility of NMES to influence the quantity and functionality of contractile proteins and mitochondria is important, as detrimental adaptations in these parameters leads to muscle atrophy, weakness and increased fatigability, skeletal muscle phenotypes that are likely at the root of cancer-related fatigue and disability and, in turn, reductions in physical activity that negatively affect long-term prognosis.

Successful completion of the proposed studies will provide mechanistic evidence for the utility of NMES to improve skeletal muscle size and function in cancer patients during treatment, which will support larger scale, randomized, control trials of its feasibility and efficacy. Specific to our investigative team, this will facilitate application of NMES to rural cancer survivors, a target population for this modality and one we are well-positioned to study. More broadly, development of NMES as an exercise modality in cancer patients could positively impact the oncology exercise rehabilitation field by providing a new, low-cost intervention that could extend the benefits of exercise to cancer patients underserved by facility-based training programs and during treatment, a time when facility-based programs are less feasible, but when detrimental muscle adaptations likely evolve. The history of NMES use within orthopedic and neurologic rehabilitation settings, its low-cost and the availability of FDA-approved devices for NMES and clinicians trained in its application (physical and occupational therapists), reduces logistical, financial and regulatory barriers to its broader repurposing for the cancer survivor population.

Purpose:

Exercise in cancer survivors is safe and has numerous health benefits (1-4). Less clear is how to disseminate the benefits of exercise to the large and growing number of cancer survivors (5, 6). In cardiac and pulmonary disease populations, this occurs primarily through facility-based programs.

However, very few of these programs currently exist for cancer survivors and participation rates in other conditions are quite low (eg, 10-20% for cardiac rehab (7)). Participation may be further hindered in cancer survivors because of limited access to exercise facilities, particularly in rural populations (8), and disease/treatment-related side-effects, such as fatigue (9). Thus, alternatives to facility-based exercise programs are needed that effectively promote an exercise training response, integrate easily into outpatient and home environments, are easy to use and require minimal costs and equipment.

Neuromuscular electrical stimulation (NMES) fulfills these criteria. An inexpensive (~\$500), hand-held NMES unit permits extracorporeal initiation of muscle contractions that can mimic resistance- or aerobic-type exercise (10), producing a training response similar to these modalities (11) with near comparable effects (12, 13). The non-volitional nature of NMES is also attractive, as cancer-related fatigue may deter motivation towards volitional exercise (9). NMES improves muscle size, strength and performance in older adults with chronic disease (14) and counteracts muscle atrophy coincident with disuse (15) and catabolic clinical conditions (16-18). Despite these beneficial effects, NMES has received almost no attention in cancer patients, where factors related to the disease (19, 20) and/or its treatment (21) may hinder exercise adaptations, although preliminary results from a case report (22) and small clinical trial (23) are encouraging.

The proposed studies are designed to determine the effect of NMES on skeletal muscle in cancer patients receiving chemotherapy, with the expectation that our results will demonstrate salutary effects on muscle morphology and function. These findings would advance the oncology rehabilitation field by providing a solid, mechanistic evidence base to support the utility of NMES as a surrogate exercise modality during cancer treatment. Such evidence would reduce the risk for failure of this modality in more definitive, randomized, controlled trials in the broader cancer population.

The proposed studies are innovative in seeking to develop effective exercise modalities for cancer survivors who are underserved by facility-based programs. They build on our seminal work describing fundamental cellular and sub-cellular deficits in skeletal muscle structure and function that contribute to disability in cancer survivors (24) by evaluating the utility of NMES to improve these same parameters. In this context, our experimental approach is also innovative in seeking to provide mechanistic evidence for the beneficial effects of NMES on skeletal muscle. We believe that this approach can economize the initial exploratory phase of developing new exercise modalities by testing the efficacy of an intervention to affect those skeletal muscle properties that are typically improved in response to exercise: size, contractility and oxidative function.

Background, Preliminary Results and Hypothesis for Aim 1

Cancer survivors often experience skeletal muscle weakness (25), due, in part, to atrophy resulting from cancer and its treatments (26). However, strength deficits exceed the loss of muscle (24, 27), due to intrinsic muscle contractile dysfunction, as our seminal work (24) showed that cancer (mostly lung) was associated with reductions in both slow-twitch, myosin heavy chain (MHC) I and fast-twitch, MHC II fiber contractility, which scaled to the whole muscle level. Whole muscle weakness, in turn, contributed to real-world disability, as it was associated with diminished walking performance (24). Our preliminary data show that functional deficits in MHC I and IIA fibers are apparent in women with breast cancer tested during chemotherapy similar to women with lung cancer from our prior work (24) and scale to the whole muscle level. In fact, contractile deficits tended to be greater in breast vs. lung cancer patients when compared to women without cancer. Our new data further show that muscle fiber atrophy and dysfunction develop during chemotherapy in lung cancer patients. Collectively, these results suggest both atrophy and intrinsic contractile deficiencies as determinants of reduced muscle functionality in breast cancer patients and identify treatment as a time when these phenotypes may evolve, emphasizing the need to identify interventions that counter muscle adaptations at this time.

NMES improves muscle size and contractile function at the whole muscle level in other diseases (14). That NMES has effects in cancer patients is supported by one trial showing a trend toward increased whole muscle strength after 4 wks of stimulation in lung cancer patients (23), although it is unclear whether these improvements were due to enhanced neural activation (28) or durable changes in muscle fiber size and/or contractility. This is an important distinction, as the former would diminish following cessation of NMES, whereas the latter would provide more lasting functional benefits. Our new data suggest that NMES directly regulates muscle fiber size and function, as it counters both single fiber atrophy and functional deterioration in older adults following total knee arthroplasty, a period

characterized by profound atrophy and dysfunction. These effects of NMES to prevent atrophy in MHC I fibers and cut atrophy in ~1/2 in MHC II fibers is remarkably similar to our data on the effects of classical training to prevent atrophy in lung cancer patients receiving treatment, suggesting NMES may function as a surrogate of classical training programs. Collectively, these data support the hypothesis that *NMES will increase single skeletal muscle fiber contractile function and size in breast cancer patients compared to patients randomized to control intervention*. Aim 1 will test this hypothesis.

Background, Preliminary Results and Hypothesis for Aim 2

Fatigue is a common side effect of cancer and its treatment, affecting a large majority of patients (29). It is multi-factorial in nature, comprising both central neural and peripheral physiological adaptations (30). One peripheral muscle adaptation that may promote fatigue is reduced oxidative capacity (31). We recently showed, for the first time in humans, that cancer and its treatment are associated with mitochondrial rarefaction (24), which we have subsequently observed in breast cancer patients studied during chemotherapy. Further compounding reductions in mitochondrial content, cancer (32, 33) and chemotherapeutic agents used in breast cancer (34) have been shown to impair mitochondrial function in pre-clinical models. Mitochondrial loss and dysfunction during cancer treatment, therefore, may contribute to cancer-related fatigue and functional disability.

Our objective of this study is to determine whether exercise training via neuromuscular electrical stimulation (NMES) has beneficial effects on skeletal muscle size and function in cancer patients. We hypothesize that NMES will improve skeletal muscle size, contractile function and oxidative capacity, based on our seminal observations in cancer patients that functional disability derives, in part, from deficits in skeletal muscle contractile protein and mitochondrial content and function, as well as our preliminary data showing that NMES counters such deficits. To test this hypothesis, we propose two specific aims:

Aim 1: Determine the effect of NMES on skeletal muscle fiber size and contractile function.

We hypothesize that skeletal muscle fiber size and contractile function will be greater in cancer patients receiving treatment who are randomized to NMES compared to controls.

Aim 2: Determine the effect of NMES on skeletal muscle mitochondrial content and function.

We hypothesize that skeletal muscle mitochondrial content and function will be greater in cancer patients receiving treatment randomized to NMES compared to controls.

Study Design:

We will use a prospective, randomized controlled design, in which recently-diagnosed, breast cancer patients (40 to 75 yrs) will be recruited (see Appendices I-VI for recruitment materials/data collection sheets) and undergo Baseline Testing during the 1st cycle of neoadjuvant or adjuvant chemotherapy. Patients will then be randomized (1:1) to 8 wks of NMES or Attention control intervention (n=12/group; Treatment Phase), with stratification for age and adjuvant or neoadjuvant chemotherapy. Following completion of the intervention, they will undergo Post-intervention Testing.

Baseline testing will include assessments of single muscle fiber size and mechanical function and mitochondrial content and function, as well as whole muscle size and contractile function and walking performance. Detailed descriptions of these assessments are provided below.

Treatment Phase Volunteers randomized to both NMES and attention control groups will receive instruction to maintain or increase their physical activity according to the clinics usual standard of care. Both interventions are described below in detail.

Post-Intervention Testing will occur in patients who complete the NMES program and controls and will include measurements identical to Baseline Testing, with post-training biopsies performed ≥ 3 d following NMES to eliminate any residual effects, per our usual protocol in other training studies that have been IRB-approved. Post-intervention testing will occur within ± 14 d from the 8 week intervention point

New methodology: Our study employs cellular and organellar level measurements of skeletal muscle structure and function. Although the methodology used in these studies is not new per se, it has not been used in the setting of exercise intervention trials in cancer patients. We feel that our approach is innovative in circumventing limitations in the detection of exercise effects at the whole body or whole muscle level due to methodological shortcomings, subjective motivation and, specific to NMES, effects on neural activation. This approach can economize the initial exploratory phase of developing new exercise modalities by more accurately characterizing the effects of such programs on those properties typically improved with exercise; namely, muscle size, contractility and oxidative function.

Procedures:

All of the procedures and interventions in this study are carried out solely for research purposes, as none are part of standard therapy/care in breast cancer patients.

Primary outcomes include: skeletal muscle fiber cross-sectional area (CSA) and function and mitochondrial content, morphology and function. Secondary outcomes include: whole muscle size/function and 6 min walk performance and indices of chemotherapy-induced peripheral neuropathy (CIPN). Procedures that will be performed on volunteers to obtain these primary and secondary outcome measures are described below.

Biopsy of the vastus lateralis (VL) will be performed, as used by our research group in a range of patient populations, including cancer patients (1), with the study leg chosen as the stronger leg in $\frac{1}{2}$ of patients and the weaker leg in the other $\frac{1}{2}$ so as not to bias adaptations based on minor functional asymmetries. Tissue will be proportioned for mechanical, immunohistochemical (IHC), mitochondrial respiratory and electron microscopy (EM) measurements, with remaining tissue frozen in liquid N₂. The VL was chosen because of its importance in determining functional disability (2) and its structural and functional deficiencies in cancer patients previously described by our laboratories (1).

Single fiber function, including tension, velocity and power, will be measured on chemically-skinned, muscle fiber segments (n \approx 25/subject/biopsy) using isotonic load clamps, as described by us (3), with data available on MHC I and IIA fibers, the two most prevalent fiber types in human muscle (1, 4).

Single fiber cross-sectional area (CSA) will be measured by IHC, as we have described (1, 3), with minor modifications to permit assessment of all MHC isoforms, as described (5).

Whole muscle contractile function will be measured, as described by us (6). Maximal peak isometric (70°, 90°) and isokinetic knee extensor torque (60 and 180°/sec) will be adjusted for thigh muscle CSA to account for variation in muscle size. Additionally, muscle fatigue will be assessed following repeated

(n=24) isometric contractions. Briefly, 24 maximal voluntary isometric contractions (2 min of intermittent contractions at 70°), following a duty ratio of 3 seconds of contraction and 2 seconds of rest. Fatigue will be defined as the average peak torque from the final 3 contractions divided by the highest peak torque achieved prior to initiation of the fatigue protocol (ie, Isometric knee extensor strength determination prior to the fatigue measure).

Thigh muscle size will be measured by dual energy x-ray absorptiometry, as described by us (1). Additionally, anthropometrics and body mass will be assessed. Height will be measured without shoes, using a stadiometer to the nearest 0.5cm. Weight will be obtained from the DEXA estimate. BMI will be calculated as weight (kg)/height(m²).

6 min walk test will be performed, as described (1), to assess changes in physical functional capacity.

Single legged stance will be performed to test balance in each leg separately. The participants place their hands on their hips then raise the 1 foot off the floor. Stance is timed until the raised foot touches the floor, the stationary foot moves, the raised foot touches the stationary leg or the hands are taken from their starting position. It is repeated three times and the best value is used. If stance exceeds 30 seconds the test will be stopped at that time.

Accelerometry will be performed, as described (6), to monitor weight-bearing activity levels, which can be used to account for possible variation in muscle use between groups (Appendix VII).

Questionnaires (provided in Appendix VIII) will be provided to assess fatigue symptoms (Fatigue Symptom Index), physical activity level (Stanford Brief Physical Activity Questionnaire), general health/well-being (MOS SF-36) and CIPN (EORTC CIPN 20).

Nerve conduction studies (NCS) will include the sural, peroneal and tibial nerves bilaterally and are the best measure of large nerve fiber function that is affected by both exercise and chemotherapy. NCS take about ten minutes and record electrical signal after providing a very mild electrical stimulus to the skin. The amplitude, distal latency, and conduction velocity will be recorded for each nerve. Study of both legs require a total of 15-20 stimulus applications, some of which are too weak to be felt.

Clinical neuropathy assessment: The Utah Early Neuropathy Scale (UENS) is a lower extremity examination performed by a neurologist that tests different modalities of strength, sensation and reflexes to detect neuropathy. It examines great toe strength, pin sensation, allodynia, vibratory sensation and Achilles reflexes in both legs.

Treatment Phase

Volunteers randomized to both the NMES intervention and control groups will receive instruction to maintain or increase their physical activity according to the clinics usual standard of care.

NMES will be carried out bilaterally on the quadriceps using a portable stimulation device (EMPI Continuum or 300PV). Study personnel will teach volunteers to use the NMES device and provide detailed directions for its use (Appendix IX). Briefly, two adhesive electrodes will be affixed to anterior surface of each thigh: ~1 cm distal to the inguinal crease and ~5 cm proximal to the patella, with the leg maintained in isometric conditions by placing a bolster under the knees and using ankle weights. Symmetrical, biphasic pulses (400 µs duration at 50 Hz) will be used, with a duty cycle of 25% (10 s on, 30 s off) at stimulation intensities sufficient to cause visible muscle contractions below pain threshold. NMES sessions will occur 5 d/wk for 1 hr/d (two 30 min or one 60 min session) for 8 wks. This regimen (lower duty cycle and 60 min/d) differs slightly from that put forth in the grant proposal in lieu of reviewer's comments on the resubmission and consultation with our co-investigator ([name]), as well as comments from volunteers in our VCC/LCCRO Pilot Project Grant, where volunteers suggested that we offer shorter sessions, as finding time for longer sessions was problematic for women with family and work commitments. We will monitor adherence to the NMES program covertly using the compliance monitoring feature built in to the NMES device software. Additionally, volunteers will self-report compliance, stimulation intensity and muscle soreness/side effects (Appendix VIII and X) and these reports will be reviewed during weekly phone contacts by study personnel. Finally, we will assess acceptability of the program using a questionnaire. These measures are taken to inform future RCTs if our hypotheses are supported.

Attention control patients will not receive an NMES device. They will receive weekly phone calls to discuss measurements of leg muscle soreness to standardize the amount of interaction with study personnel to the NMES group.

1. [name], M. J., Miller, M. S., Callahan, D. M., Sweeny, A. P., Nunez, I., Grunberg, S. M., Der-Torossian, H., Couch, M. E., and [name], K. (2013) Molecular mechanisms underlying skeletal muscle weakness in human cancer: reduced myosin-actin cross-bridge formation and kinetics. *J Appl Physiol* **114**, 858-868

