Our primary goal is to assess the effect of NMES on: single fiber tension (force/CSA), velocity and CSA and mitochondrial content and ADP-stimulated oxygen consumption rate. A general linear mixed model will be used, with treatment group as between-subject and time as within-subject effects. A random effect will be included to account for clustering of observations within subjects (ie, fibers within each subject), as described (1), with the model conceptualized as a multi-level analysis with single fiber/organellar-level outcomes comprising level 1 variables and person-level covariates comprising level 2 variables (2). Covariates (eg, stage, chemotherapeutics, and activity level) can be included in the model as level 2 variables to control for potential confounders that differ by group. Whole muscle size and function and 6 min walk performance will be used in secondary analysis to evaluate whether changes in myofilament or mitochondrial content or function scale to variation in tissue-level or whole body function or size, as we have previously observed that molecular- and organellar-level function scale to the tissue and whole-body level in cancer (3), aging (4) and chronic disease (5).

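### The primary single-fiber model has no term for fiber type and no analysis by type, although type is recorded and the plan's own data show NMES effects on fiber size that differ by type

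*Combined protocol and SAP*

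**What the plan says.** The Statistical Analysis Plan names three single-fiber primary outcomes: tension, velocity and cross-sectional area (CSA). The model is stated once: "A general linear mixed model will be used, with treatment group as between-subject and time as within-subject effects". To this it adds: "A random effect will be included to account for clustering of observations within subjects". The levels are defined as "single fiber/organellar-level outcomes comprising level 1 variables and person-level covariates comprising level 2 variables", and the only adjustment mentioned is at person level: "Covariates (eg, stage, chemotherapeutics, and activity level) can be included in the model as level 2 variables".

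Fiber type belongs to the individual fiber, so it is a level-1 variable and falls outside everything listed. No section gives a type term, a type interaction, separate models by type, or a quota of fibers by type. The sample size paragraph gives one 20% difference for tension and one for CSA, neither split by type.

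Elsewhere the plan treats type as important. Under Procedures, single-fiber function is measured on about 25 fibers per subject per biopsy, "with data available on MHC I and IIA fibers, the two most prevalent fiber types in human muscle". CSA is measured separately by immunohistochemistry, adapted so that every MHC isoform can be assessed. The Aim 1 background calls MHC I slow-twitch and MHC II fast-twitch. It also summarises the team's knee arthroplasty data: "These effects of NMES to prevent atrophy in MHC I fibers and cut atrophy in ~1/2 in MHC II fibers".

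**The concern.** Tension and velocity come from a small sample of fibers. If the two types differ in level, the mean of a biopsy moves with the share of each type among its 25 or so fibers. The subject random effect absorbs a person's stable mix, but not the change in sampled mix between the baseline and post-intervention biopsies. That change adds noise to every within-subject difference. If the mix sampled after NMES also moved systematically relative to control, the pooled mean would move with no change inside either type. Aim 1 asks about contractile function of the fibers, so the two explanations need to be separable.

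Velocity is the clearest case, because the plan names the types by their speed. For CSA the issue is different: a single pooled effect would average responses that the plan's own data suggest are unequal.

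**Working it through.** **Inputs from the documents.** 12 per group, a 20% difference, 90% power, 5% significance (Statistical Analysis Plan); about 25 fibers per biopsy (Procedures).

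**Assumptions, since the documents are silent.** Two-sided test; a 50:50 mix of MHC I and IIA; IIA/I ratio R of 1.2, 1.5, 2 or 3; the same total number of fibers at both biopsies.

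**Step 1: the plan's own figure.** No SD is stated, so n=12 cannot be reproduced; only the SD it implies can be recovered. With the noncentral t on 22 df, 90% power at 12 per group needs a standardised difference of 1.385, so SD = 20/1.385 = 14.4%. (The normal approximation gives 1.323 and 15.1%.) Below, 14.4% is taken as the SD of the within-subject change, free of mix noise.

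**Step 2: noise from type sampling (tension and velocity).**
- SD of the sampled IIA share: sqrt(0.5 × 0.5 / 25) = 0.10.
- Difference between types as a fraction of the pooled mean: D = (R − 1) / ((R + 1)/2).
- SD added to a pre-post change: D × 0.10 × sqrt(2).
- Total SD: sqrt(14.4² + added²). Power is then recomputed at 12 per group.

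| IIA/I ratio | D | Added SD | Total SD | Power | n per group for 90% |
|---|---|---|---|---|---|
| 1.2 | 18.2% | 2.6% | 14.7% | 89% | 13 |
| 1.5 | 40.0% | 5.7% | 15.5% | 86% | 14 |
| 2 | 66.7% | 9.4% | 17.2% | 78% | 17 |
| 3 | 100% | 14.1% | 20.2% | 64% | 23 |

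This counts random sampling of fibers only. If the true share also varied between biopsies with an assumed SD of 0.10, power would be 88%, 81%, 67% and 48%.

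**Step 3: when a false effect arises.** If the IIA share in one arm rises by 10 points with no change inside either type, the pooled mean shifts by 0.10 × D: 1.8%, 4.0%, 6.7% or 10.0% at the four ratios. A simulation (4,000 trials per setting, 12 per group, 25 fibers per biopsy, SD of the share 0.10, t-test on subject changes) gave these rejection rates with no within-type effect:
- No systematic shift: about 5% for the pooled analysis.
- A 10-point shift: 6%, 9%, 12% and 16% for the pooled analysis.
- Type-standardised analysis, whatever the shift: 4.3% to 5.5%.

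**Step 4: CSA.** No fiber count is stated for the immunohistochemistry, so Step 2 does not carry over. Instead, take the arthroplasty pattern literally: 100% protection from atrophy in MHC I and 50% in MHC II. If atrophy without NMES were equal in the two types, a pooled analysis would show (1 − p) × 100% + p × 50%, where p is the type II share. That is 85%, 75% or 65% at p = 0.3, 0.5 or 0.7. The pooled answer describes neither type and changes with the mix.

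**Step 5: if separate analyses are intended.** Three outcomes by at least two types make at least six tests, with no rule for combining them. As an illustration, two independent 5% tests per outcome give 1 − 0.95² = 9.75% for at least one false positive.

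**The case against.** The strongest reply is that the plan never says the fibers will be pooled. It is silent on type, its covariate sentence is permissive and bars no level-1 term, and it discusses fiber data by type throughout the background. The clustering model is attributed to earlier published work, which may have analysed types separately. This stands as far as it goes: a reader might infer a decision to pool, and the documents do not support that. What they show is a concrete primary model from which a recorded fiber-level variable is absent. The citation is attached to the random effect, and what is left to a citation is not prespecified here.

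The power figures are also open to challenge. If the planners' SD came from pooled fibers, mix noise is already inside it and the 90% is not reduced. If it came from type-specific data, that hints that analysis by type was intended. The loss in Step 2 needs a within-type SD together with a pooled analysis, and the documents do not settle this. At a ratio of 1.2 the loss is trivial.

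Finally, the evidence that NMES acts differently by type concerns fiber size after knee arthroplasty. It does not show a type-specific effect on tension or velocity, nor any effect in breast cancer patients.

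**Conclusion.** The point holds as a gap in the primary analysis: followed as written, the model yields an answer for tension and velocity that depends on the sampled type mix, and one for CSA that can mask type-specific responses. If separate analysis is intended, the rule for deciding Aim 1 is missing instead.

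The size is conditional. With a within-type SD of 14.4%, a 50:50 mix and random sampling of 25 fibers, power for a 20% difference is about 89%, 86%, 78% or 64% at IIA/I ratios of 1.2, 1.5, 2 or 3. The last case is a threefold ratio and should be read as the far end of the range.

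Two stronger readings should be resisted. One is that the trial is underpowered: that cannot be concluded without the SD and the type difference, and neither is given. The other is that an apparent gain in contractility would be an artefact of fiber mix: random mix leaves the false-positive rate near 5%, bias needs a systematic difference between the arms in how the mix changes, and no section reports one.

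**What to change.** In the Statistical Analysis Plan:

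- Add fiber type as a level-1 fixed effect with its interactions with group and time, or prespecify separate models by type.
- Report the NMES effect by type for tension, velocity and CSA. For CSA, say how each isoform measured is handled, not only MHC I and IIA.
- For each Aim 1 outcome, state the single contrast across types, or the multiplicity rule, that decides it. How the types are weighted is the sponsor's choice of estimand; equal weighting is one option and nothing in the documents requires it.
- State the SD behind n=12 and whether it is within type or pooled, so that the power statement matches the analysis.

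The cost is SAP wording, a few more model parameters and slightly more output. The plan already expects data by fiber type, so no new measurements are needed.
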